9. MECHANISTIC ASSAYS

Subjects may have blood drawn and saliva collected for laboratory studies at the discretion of the investigator throughout the study. The investigator will document in the database the rationale for each sample. Examples include: checking mechanistic studies for subjects who develop specific gastrointestinal side effects (e.g. EoE), subjects who are unable to tolerate desensitization to 300 mg or subjects with severe adverse events.

The overall goals of the mechanistic studies are to identify changes in basophil, T cell, and antibody responses using peripheral blood and saliva samples from study subjects. We are especially interested in the changes in these immune compartments that are associated with treatment with oral immunotherapy for food allergy. In other words, we aim to explore the mechanisms responsible for long-term desensitization and/or tolerance to

food allergens induced by immunotherapy. Delineating its specific long-term effects on the immune reaction will enable us to determine its utility and define its therapeutic role.

We have previously demonstrated changes in peanut-specific IgE, IgG, and IgA, as well as changes in basophil activation and T cell phenotypes in subjects on immunotherapy. Peripheral blood samples from subjects will be collected in this protocol to further follow these subjects' immune responses to the food.

Blood collected in serum separator tubes will be centrifuged and serum collected and stored at -80°C until use. Serum will be used to study allergen-specific IgE, IgG, and IgA quantities, epitope specificity, and blocking function. Blood collected in heparin-containing tubes will be used to isolate peripheral blood mononuclear cells (PBMCs) using a Ficoll gradient. PBMCs will be stimulated *in vitro* with allergens and used to assess changes in T cell frequency, phenotype, and function. Heparinized blood will also be used to determine basophil activation responses by *ex vivo* stimulation and assessment via flow cytometric techniques.

Saliva will be assessed for total and allergen-specific IgA and Secretory-IgA (sIgA) quantities. Saliva samples will be frozen at -80°C until analysis.

10. STATISTICAL CONSIDERATIONS AND ANALYSIS STRATEGY

A. INTERIM AND FINAL ANALYSES

An interim analysis will be performed when at least 50 patients have finished their peanut OIT treatment phase and at least 25 patients finished 6 months of food equivalent treatment phase.

The interim analysis and the final analyses will include all subjects in the study who provided complete follow up information regarding their

compliance and adverse events, and will also include those who dropped out or were withdrawn from the study before its completion.

The final analyses will be performed when all subjects have completed the study.

B. PLANS FOR EACH SPECIFIC AIM

Aim 1. Investigate the safety and compliance in the 2-stage protocol in subjects who either (a) have previously developed desensitization and then subsequently lost this protection due to a period of time off of therapy, or (b) have previously endured an extended time on placebo therapy.

We will rely on the following methods to accomplish Aim 1:

1. Our primary analysis will focus on estimates of incidence rates of adverse events and the proportion of days of treatment missed during the treatment protocol.
2. Our secondary analyses will include estimation of
 - the overall incidence rate of gastrointestinal AEs during the entire 2-stage treatment sequence.
 - the overall incidence rate of Epipen use
 - the overall incidence rate of drop-outs due to gastrointestinal AEs during the entire 2-stage treatment sequence.
3. Exploratory analyses will be used to investigate potential candidate risk factors for AEs (using logistic regression models) and causes of missed treatment days (using generalized log-linear models for counts of days).
4. Descriptive tabular and graphical methods will be used to visualize the data and examine the relationships among the measures of interest using graphical and descriptive methods.

All statistical estimates will be tabulated with the corresponding 95% confidence intervals (CI). Interpretation of these CIs will be an integral part of the analyses. For Aim 1 (and for all the aims) sensitivity analyses will be performed to evaluate the robustness of the main results to reasonable perturbations of the choices of statistical methods and statistical assumptions used. For example, the influence of any extreme or questionable data value will be explored. Results of the sensitivity analyses will only be used to guide our level of confidence in the main results.

Aim 2. Characterize and compare the two stages of the protocol in terms of safety and compliance.

We will rely on the following methods to accomplish Aim 2:

1. Our main analyses will focus on stage-specific estimates of incidence rates of adverse events and the proportion of days of treatment missed.

Comparisons of the two stages will rely on logistic regression models for rates, and generalized log-linear models for counts of days. The primary emphasis will be on point estimates and confidence interval estimates. No hypothesis tests will be performed.

2. Our secondary analyses will include estimation of

- the stage-specific incidence rates of gastrointestinal AEs during the entire 2-stage treatment sequence.
- the stage-specific incidence rates of Epipen use
- the stage-specific incidence rates of drop-outs due to gastrointestinal AEs.

Comparisons of the two stages will rely on logistic regression models for rates, and generalized log-linear models for counts of Epipen usages. The primary emphasis will be on point estimates and confidence interval estimates. No hypothesis tests will be performed.

3. Exploratory analyses will be used to investigate potential candidate risk factors for AEs (using logistic regression models) and causes of missed treatment days (using generalized log-linear models for counts of days).

4. Descriptive tabular and graphical methods will be used to visualize the data and examine the relationships among the measures of interest using graphical and descriptive methods.

Statistical estimates of interest include stage-specific parameter estimates (e.g., incidence rates) as well as estimates of differences between stage-specific parameters (e.g., odds ratios, or rate differences). All statistical estimates will be tabulated with the corresponding 95% confidence intervals (CI). Interpretation of these CIs will be an integral part of analysis. For Aim 2, sensitivity analyses will be performed to evaluate the robustness of the main

results to reasonable perturbations of the choices of statistical methods and statistical assumptions used.

Aim 3. Explore the mechanisms responsible for long-term desensitization and/or tolerance to food allergens induced by immunotherapy.

We will rely on the following methods to accomplish Aim 3:

1. Our main analyses will focus on changes in basophil, T cell, and antibody responses in peripheral blood and saliva samples. The exploratory analyses will be used to generate or refine hypotheses. No hypothesis tests will be performed.
2. Descriptive tabular and graphical methods will be used to visualize the data and examine the relationships among the measures of interest using graphical and descriptive methods.

All statistical estimates will be tabulated with the corresponding 95% confidence intervals (CI). Interpretation of these CIs will be an integral part of analysis of the primary outcome.

For Aim 3, sensitivity analyses will be performed to evaluate the robustness of the main results to reasonable perturbations of the choices of statistical methods and statistical assumptions used.

C. CHOICE OF SAMPLE SIZE

The choice of sample size is based entirely on the ethical necessity of providing therapy to a pre-defined number of individuals in need of salvage therapy. We anticipate that up to 100 eligible subjects will be enrolled to receive the proposed salvage treatment regimen.

11. DATA MANAGEMENT AND DATA HANDLING:

A. RESEARCH DATA MANAGEMENT

Management of the research data for this study will involve collection, entry, processing, storage, retrieval, archival, distribution and documentation of

information collected according to a written protocol. The overall strategy for quality assurance in data management will be of a professional level as described in the following sections.

B. PLAN FOR ENSURING CONFIDENTIALITY

Study records will be kept confidential as required by law and institutional policies. All research data and records are stored in the Food Allergy database, on the UNC Pediatric Allergy / Immunology server, and/or research study binders. Participants' personal identifying information will be accessible only to the investigator and authorized study personnel. Research data will be identified only by study identification numbers (IDs). These study IDs will be used to maintain relationships in the data between various tables. All consent forms and any paper data collection instruments will be stored in a locked cabinet in a secure location. The list identifying subjects with their contact information will be kept separate from the scientific study data. The database will be created within centralized files and maintained on University approved, encrypted, password protected, shared research drives and will be viewed only on approved devices by approved study personnel. To ensure PHI Security, procedures to maintain privacy and confidentiality will be followed rigorously. For each subject, identifying information and protected health information (PHI) will be collected along with scientific study data. Each research subject will be assigned a study identification number (ID). The scientific study data will be stored in a digital file that does not include patient identifiers or PHI. A separate data file will contain identifiers and PHI. A master file linking patient identifiers to the study data will be kept under lock and key by principal investigator. The database will be password protected and will be stored on servers housed in a secure location.

C. PLAN FOR ENSURING DATA SECURITY

The research binders, including source documents, are kept locked in the study team's office suite. The subject's information is accessible only to the investigator and authorized members of his designated research study team by password protection or direct viewing of the research record.

D. PLAN FOR QUALITY ASSURANCE

The investigators will keep accurate records to ensure that the conduct of the study is fully documented. The investigator is responsible for regularly reviewing the conduct of the trial, for verifying adherence to the protocol, and for confirming the completeness, consistency, and accuracy of all documented data. The P.I. will have overall responsibility for ensuring quality in the data and in the procedures that produce the data. In addition to the master protocol document, written guidelines and detailed procedure manuals may be needed for uniform adherence to the detailed intent of the protocol. The written record of how the study was performed will be completed prior to commencement of recruitment and will be updated during the course of the study. The P. I. will have overall responsibility for the definition and production of the documents necessary to describe all aspects of the study in sufficient detail to insure the study can be conducted in a scientifically sound, standardized manner. The P.I. will be assisted by members of the research team in monitoring adherence to protocol.

E. DATA HANDLING PROCEDURES

Case Report Forms (CRFs). As it is not unusual for revisions to the CRFs to occur in clinical studies, each form will be clearly labeled with a version number. Transition to an updated version of a CRF will be communicated to all members of the research team.

Data Collection. Study data will be recorded at the point of care using data collection instruments provided by the study team. Paper forms will be stored in a designated folder securely maintained at the point of care and will be retrieved by the study team on a daily basis. The subjects' medical records will be retrospectively reviewed to obtain study data and the patient characteristics at admission. The medical record data will be recorded on a patient-specific CRF. Data collection will adhere to precise written instructions and will be monitored to insure adherence to the protocol.

Data Entry. All data entered into the database from the CRFs will be verified by comparing the original CRFs to the values in the database.

Data Editing. The P.I. will be responsible for reviewing data-monitoring results and investigating questions raised (i.e., "queries") about remarkable or questionable data values.

Database Documentation. The names of the variables and their valid ranges or categorical values will be listed in a "data book". Documentation will also include an index of computer programs and an index of reports. All programming for statistical computation will include comments providing internal documentation.

Pilot Testing of Operations. All aspects of data management and project operation will be pilot tested prior to the commencement of the study in order to verify adequacy of the methods, materials and systems prepared. Every clinical study collects such pilot data –either intentionally prior to commencement of the study, or unintentionally after recruitment has begun.

F. RISK OF DEDUCTIVE DISCLOSURE

We will minimize the risk of unauthorized persons using the database to figure out a subject's identity and responses.

(1) The database will comprise two separate files: a TRACKING FILE (containing sensitive patient identifiers such as name, birthdate, date and time of admission to the ER, and Subject_ID) and a de-identified RESEARCH FILE containing non-sensitive data such as Subject_ID, age at admission to the ER, elapsed time since admission to the ER, treatment assignment, pain scores, questionnaire data, etc. Both database files contain Study_ID. This allows the two sets of information to be linked together if necessary, but prevents linkage as long as the two files are kept safely separated.

(2) The database will be secured on encrypted storage media to guard against hacking or other unauthorized access. Paper forms will be stored in locked locations.

(3) Data will be retrieved from the RESEARCH FILE and distributed to specific personnel (e.g., the P.I., or co-investigators) for purposes of statistical computations for preparation of publications. Storage, retrieval and distribution will be carefully and securely controlled. Digital

transmission of the data will be encrypted. Transportation of the data will use secure media.

(4) Selective data-entry will also be employed: Some of the study data does not need to be entered into an electronic file and will be maintained on paper forms in a locked storage location.

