6. The participant experiences severe symptoms during the build-up or maintenance phases as a result peanut OIT dosing

7. In the investigator's discretion, there is poor compliance or any other concern that would create an unacceptable risk to the subject.

8. The participant dies.

9. The study ends.

To the extent possible, participants who discontinue therapy will be followed to observe and record study outcomes.

D. STUDY TERMINATION CRITERIA

If any of the stopping rules listed below are met, study enrollment will be suspended, the initial dose escalation phase and build-up phase will be stopped, and all enrolled participants will remain on their current dose pending expedited review of all pertinent data by the Data Safety Monitoring Board:

1. Any death related to peanut OIT dosing.
2. More than one event comprising systemic allergic symptoms with significant hypotension at any stage of the protocol.
3. More than 3 participants require more than 2 injections of epinephrine during dosing of the peanut product.
4. More than 3 of the following events:
 - Severe adverse event, other than anaphylaxis, related to investigational product.
 - Eosinophilic esophagitis.

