5. STUDY DESIGN AND SCHEDULE

A. LOCATION

Visits will be done at the University of North Carolina-Chapel Hill Food Allergy Study Center (FASC), located in the CTRC building. The FASC is equipped as a clinic. In addition to MD and NP coverage, there are 24-hour adult and pediatric rapid response teams in case of emergencies. The study

site is adjacent to the UNC Hospitals Emergency Department where subjects can be transferred for continued monitoring and acute care as needed.

B. DURATION OF ENROLLMENT

The study enrollment duration is for 2 years or until a commercial peanut OIT products is available to participants whichever is sooner.

C. DURATION OF THE STUDY PER PARTICIPANT

Each participant will be in the study for a total of 12 months. There will be three phases in the study: escalation phase for 1 day, build up phase up to 16 weeks, and maintenance phase up to 3 months on peanut OIT followed by 6 months of food equivalent to tolerated peanut protein.

D. STUDY VISITS

Participants will have: an initial study visit (screening), followed by one visit for the escalation phase, followed by visits every 1-2 weeks for the up dosing phase, a visit at the end of peanut OIT treatment at 6 months, a phone interview at 9 months and a final visit at the end of the study at 12 months. The screening visit may be combined with the initial escalation visit.

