5. PEANUT FOOD EQUIVALENT PHASE

At the end of maintenance peanut OIT phase, subjects will be given instruction during their last study visit in maintenance phase to start a peanut food equivalent of 300 mg peanut protein: which include the following options: peanuts (not dry roasted), peanut butter, powdered peanut butter, mini snickers, mini Reese's cup, cheese peanut butter crackers, Reese's pieces, Reese's peanut butter chips or Goober. An instruction sheet will be provided on how much to take of one of these products on a daily basis. This phase will last for 6 months. During this phase, subjects will continue to fill compliance sheets and they will receive phone calls from study coordinators at 9 months. This will be no study visits until the end of this phase to hand daily compliance sheets and fill a survey. At the end of the study the subjects may have the option to enroll in our peanut OIT follow up study if study investigator deemed they meet inclusion criteria for the study.

E. HANDLING ADVERSE REACTIONS AND FOLLOW UP DURING HOME DOSING

Each subject is given multiple ways to contact study staff when they are enrolled in the study. This is reviewed at the end of each visit. The families are told to contact the study staff if they have any questions or concerns before the next visit or at any time during the study. Study contact information given to families include the research clinic phone number, email addresses and office numbers of the, study coordinators, and instructions for how to get in contact with the pediatric on-call allergist who can reach the lead coordinator if needed. Subjects who have any symptoms during observed dosing, or those who express any specific concerns are given a follow up phone call on the day after dose escalation. All subjects will be asked to carry an auto-injector epinephrine. If prescription is not provided by their physician, we will provide them with a prescription for an auto-injector epinephrine. We will ask subjects to fill their prescription and

bring their epinephrine auto-injector with them before starting treatment to verify they have filled their prescription.

F. MANAGING MISSED DOSES

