Subjects who miss one to two days of the daily dose will continue at their current dose at home. The PI will determine where the next dose of study protein is given for those who miss three to four days of the daily dose based on the length of time on study, the daily dose amount, the subject's reaction history and the amount of time since the last reaction to a dose in order to assure safety with dosing. Those who miss more than four consecutive days will return to the clinical research unit for evaluation by the study team in order to determine the best course of action for the subject. Options open to the investigator include repeat desensitization, observed dosing at the current level, or observed dosing at a dosing level previously tolerated by the subject. All such management of missed doses will be carefully documented in the study database.

G. MONITORING OF SIDE-EFFECTS, ADVERSE EVENTS, AND CLINICAL CHANGES

- We will monitor accidental reactions to peanuts in each subject during each visit to the study center. We will note any reaction that occurs in a subject within two hours after the ingestion of peanuts, and record the type of symptoms (i.e., skin, respiratory, gastrointestinal, or cardiovascular). A copy of the CRF is in the appendix.
- To monitor subjects for adherence, any accidental ingestion, any symptoms related to daily dosing and any unintended side-effects of daily dosing, the families will be asked to keep a simple daily diary to record the requested information. A copy of the daily diary is included in the appendix of the protocol.
- We will check mechanistic changes in the immune system by checking lab tests, skin testing or spirometry during the study.

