Afterwards, if clinical indicated, spirometry will be administered per clinic asthma standard of care as an assessment of lung function in subjects 7 years of age or older during study visits. Procedures follow American Thoracic Society criteria. Bronchodilation is not conducted and beta-agonists do not need to be withheld prior to the test. The test is administered while the subject is in a standing position and using a nose clip. We will reference the Hankinson predictive values for lung function. Subjects between 7 and 11 years who are unable to perform spirometry will be offered an attempt to use a peak flow meter. Participants who are unable to maintain >80% PEFR of their predicted value will need to be evaluated by the NP or MD before proceeding.

E. SALIVA COLLECTION (OPTIONAL-SUBJECT TO THE INVESTIGATOR DISCRETION)

A 0.5 ml of saliva could be collected to run mechanistic assays as determined by the investigator. Examples include: checking mechanistic studies for subjects who develop specific gastrointestinal side effects (e.g. EoE), subjects who are unable to tolerate desensitization to 300 mg or subjects with severe adverse events.

Samples may be obtained by the subject spitting independently or the coordinator using a plastic syringe to gather saliva.

F. COMPLIANCE SHEETS

Subjects will be given sheets to record their compliance with the medication that needs to be changed on a weekly basis. The sheets will also include reactions the subjects have, the symptoms they experienced and how they were treated. Subjects will hand the sheets to their study coordinator at each visit and at the end of the study. The data from these sheets will be used to assess compliance and adverse events in addition to information gathered from subjects from their follow up surveys.

G. URINE PREGNANCY TEST

All participating females of child bearing age will have pregnancy urine test in screening then for the last follow up visit within 30 days of the last pregnancy test. Female subjects who become pregnant will be taken out of the study. Sexual abstinence will be accepted as an effective method of

contraception.

Sexually active female subjects are to use either:

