For additional information and a printable version of the NCI-CTCAE manual, consult the NCI- CTCAE website,

<http://ctep.cancer.gov/reporting/ctc.html>.

D. ADVERSE EVENTS COLLECTION PROCEDURES

The Principal Investigator is responsible for collecting and recording all clinical data. As these results are collected, all toxicities and adverse events will be identified and reported as described above. The Principal Investigator will determine relationship of the event to the study activities and decide the course of action for the study participant.

Adverse events will be evaluated from the onset of the event until the time the event is resolved or medically stable or until 30 days after reporting of the event, whichever comes first.

Adverse events may be discovered through any of these methods:

1. Observing or questioning the participant during study visits.
2. Reviewing the forms given to the patient for home monitoring and documenting compliance.
3. Receiving an unsolicited complaint from the participant.

E. SERIOUS ADVERSE EVENT NOTIFICATION

The research staff will notify the principle investigator of any serious adverse event immediately on learning about the event. Serious adverse events will be recorded on the adverse event CRF within 24 hours of their occurrence. The following attributes must be assigned:

- Description
- Date of onset and resolution (if known when reported)
- Severity
- Assessment of relatedness to test procedure
- Action taken

The principal investigator must apply their clinical judgment to determine whether an adverse event is of sufficient severity to require that the subject be removed from treatment. If necessary, an investigator must suspend any trial procedures and institute the necessary medical therapy to protect a subject from any immediate danger.

Subsequent review by the DSMB or IRB may suspend further treatment or procedures. The DSMB retain the authority to suspend additional enrollment and treatments as applicable.

A subject may also voluntarily withdraw from the study due to what he/she perceives as an intolerable adverse event, or for any other reason. If

voluntary withdrawal is requested, the subject should be asked to complete a study termination form, and be given appropriate care under medical supervision until the symptoms of any adverse event resolve or their condition becomes stable.

F. NOTIFYING THE IRB AND DSMB

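### Read literally, the Section 10.A analysis set keeps every drop-out but leaves out participants who finish with gaps in their compliance or adverse-event data

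*Combined protocol and SAP*

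**What the plan says.** Section 10.A contains the only analysis-set rule in the document, and it serves both the interim and the final analyses. It has two limbs. The first reads "The interim analysis and the final analyses will include all subjects in the study who provided complete follow up information", and the sentence goes on to tie completeness to compliance and adverse events. Under the second, the analyses "will also include those who dropped out or were withdrawn from the study before its completion", with no condition on how much data those people supplied.

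The word complete is not defined. No all-treated or safety set is named, and no rule says how an unrecorded dosing day is to be counted.

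The set feeds both primary outcomes in Section 3.B (adverse-event incidence and days of treatment missed) and the secondary outcome of drop-out due to gastrointestinal adverse events.

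On data sources, Section 6.F says of the participant-kept sheets: "The data from these sheets will be used to assess compliance and adverse events in addition to information gathered from subjects". In the six-month food-equivalent phase, Section 5.D.5 says: "This will be no study visits until the end of this phase to hand daily compliance sheets and fill a survey". Section 5.D lists, after the 6-month visit, "a phone interview at 9 months and a final visit at the end of the study at 12 months".

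**The concern.** The completeness condition applies only to people who did not leave. A finisher with gaps therefore meets neither limb, whereas a drop-out with the same gaps, or worse, is analysed. Gaps are plausible: the sheets are kept at home, and in the second stage there is one phone contact and no visit until the end.

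The study is single-arm and plans no hypothesis tests, so its product is a set of estimates with confidence intervals, and the denominator matters. Removing finishers but no drop-outs must raise any drop-out proportion computed on the set. If incomplete sheets go with poorer adherence, missed days among finishers would look fewer than they were. Two analysts could also build different sets from the same sentence.

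**Working it through.** **1. Who is in.** Apply the rule (complete follow-up, or dropped out or withdrawn) to the four possible cases.

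| | Complete data | Gaps |
|---|---|---|
| Finisher | in, first limb | in neither limb |
| Drop-out or withdrawn | in, second limb | in, second limb |

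Exactly one case falls out.

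**2. Interim.** Section 10.A triggers the interim once at least 50 participants have finished the OIT phase and at least 25 have finished the food-equivalent phase. At those minimum counts, 50 - 25 = 25 people have finished OIT but not the food phase. Any of them still on treatment fits neither limb if complete means 12 months, as does anyone still in the OIT phase. If complete means up to date at the data cut-off, they are in. The text does not say which.

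**3. Drop-out for gastrointestinal adverse events.** The plan gives no figure to reproduce and no drop-out or incompleteness rate, so all inputs here are assumed. Let d be true all-cause drop-out among treated participants, f the share of finishers with incomplete data, and g the true proportion dropping out for gastrointestinal adverse events. All drop-outs stay in the numerator, and (1-d)f of those treated leave the denominator:

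reported proportion = g / [1 - (1-d)f]

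Per 100 treated, with d = 20% there are 80 finishers.

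- f = 10%: 8 left out, 92 analysed; g = 5% reads as 5/92 = 5.4%.
- f = 40%: 32 left out, 68 analysed; g = 5% reads as 5/68 = 7.4%.
- g = 10% over the same range of f reads as 10/92 = 10.9% to 10/68 = 14.7%.

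The result is not very sensitive to d. For g = 5% and f = 10-40%, d = 10% gives 5/91 = 5.5% to 5/64 = 7.8%, and d = 30% gives 5/93 = 5.4% to 5/72 = 6.9%.

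**4. How f depends on the definition.** Suppose complete meant every weekly sheet over 52 weeks, each independently missing or incomplete with probability q. Then f = 1 - (1-q)^52. Assumed q of 0.1%, 0.5% and 1% give f of 5.1%, 22.9% and 40.7%. The documents do not give q. This shows only that a strict definition makes f sensitive to small lapses.

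**5. Missed days among finishers.** Suppose a quarter of finishers have gaps and miss 10% of days, against 5% for the rest (assumed). The true figure for finishers is 0.75 x 5% + 0.25 x 10% = 6.25%, but the analysed finishers show 5.0%. If both groups miss equally, there is no bias. For the whole analysed set, removing finishers also gives drop-outs more weight, which could pull the other way.

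**The case against.** The strongest reply is that the sentence only includes people and excludes nobody. It can be read as those who completed follow-up plus those who did not, which is everyone. That may well be what was meant, and a reader should not infer that the sponsor intends to remove finishers. But the benign reading leaves the completeness condition with no work to do, and nothing else in the document settles the matter.

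The second reply is that few people are affected, and much of it stands. Section 4.C item 2 lets participants lost to follow-up be withdrawn, so someone who never returns with second-stage sheets can enter by the second limb. The same section allows withdrawal at the investigator's discretion where "there is poor compliance or any other concern that would create an unacceptable risk to the subject", and those people are included too. The sheets are also not the only source. Section 8.D lists "Observing or questioning the participant during study visits" and unsolicited complaints, Section 6.F adds surveys, and Section 5.F states: "All such management of missed doses will be carefully documented in the study database". These can recover events and managed lapses. They do not clearly replace a daily record, since under 5.F one or two missed days simply continue at home. An assumed 40% of finishers incomplete has no support in the documents and should be read as an outer case.

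The third reply is that the plan already promises sensitivity analyses (10.B) and investigator checks of completeness (11.D). The sensitivity text is generic, its only example concerns extreme or questionable values, and it says the results serve only to guide confidence in the main results. Neither provision changes who is in the primary set.

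The fourth reply is that the effect is small beside sampling error, which is fair. For 5 of 100, the exact 95% interval is about 1.6-11.3%, so even 7.4% lies inside it. The inflation is nonetheless systematic, and the interval does not allow for it.

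**Conclusion.** The gap is real and should be fixed. As written, the rule gives a selective set: finishers with gaps are left out by omission, drop-outs with gaps are kept, and participants still on treatment at the interim are left out if complete means 12 months. Confidence is medium, because the sentence also bears a benign reading.

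The one effect with a certain direction is an inflated drop-out proportion, if any finisher is left out. For the listed outcome, drop-out due to gastrointestinal adverse events, a true 5% reads as 5.4-7.4% under 20% all-cause drop-out and 10-40% of finishers incomplete, all assumed. Missed days among finishers are understated only if gaps go with poorer adherence.

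A reader might infer three stronger conclusions that the documents do not support:

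- **That the primary outcomes are biased by a known amount or in a known direction.** No figure or overall direction can be derived for missed days, and none for adverse-event rates.
- **That inflation of all-cause drop-out distorts a listed outcome.** Section 3.A mentions drop-outs as an objective, but the only drop-out outcome in 3.B is the gastrointestinal one.
- **That safety oversight suffers.** Under Section 8.F the DSMB receives listings of all adverse and serious adverse events, whatever the analysis set. The harm is confined to the reported estimates.

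**What to change.** Replace the analysis-set sentence in 10.A with: *The interim and final analyses include every participant who took at least one dose, whether or not their follow-up information is complete.* This settles the interim question as well.

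Add two short rules:

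1. Use all treated participants as the denominator for drop-out.
2. Treat unrecorded dosing days up to discontinuation, scheduled end of treatment or the data cut-off, whichever comes first, as missing data. Report all-taken and all-missed bounds as one of the sensitivity analyses that 10.B already promises.

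The adverse-event models in 10.B need not change for this point.

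The cost is slightly more analysis work and a wider reported range for missed days; no new data are needed. Among finishers the bounds differ by f times the unrecorded share of the course. If 10-40% of finishers (assumed) lacked 3 of 12 months of sheets, the width would be 0.10 x 3/12 = 2.5 to 0.40 x 3/12 = 10 percentage points. That uncertainty would be present anyway; leaving these finishers out would hide it.
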